## 1.8 Hypothesis 4: Self-efficacy

*H4: Individuals assigned to the High intervention levels for Tech and Touch will demonstrate higher levels of self-efficacy.*

### 1.8.1 Outcome 1 – Self-efficacy

*Outcome specification:* The self-efficacy scale was scored as the mean of six individual 5-point Likert scale survey items and was promulgated in each of the surveys (i.e. Admission, 15-day Post-discharge, 6-month Post-discharge). The six items were:

1. I am confident I can change my behaviors to improve my health.
2. I am confident that I can work with my provider to improve my health.
3. I am confident that if prescribed a new medication, I can take it appropriately.
4. I am confident that I can do the different tasks and activities needed to manage my health condition(s).
5. I am confident that I can keep symptoms or health problems from interfering with the things I want to do.
6. I am confident that I know how to take care of my health.

*Statistical Model:* OLS regression model with and without an interaction of Tech and Touch were reported.

*Covariates:* No covariates were added to this analysis.

*Sub-sample analysis:* No sub-sample analyses were considered for this outcome.

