3.1.3 Allocation ratio

The Tech intervention contrasted two function sets—Lite-Tech (40% allocation), which was a minimalistic toolset focused on providing basic data to the patient, and Full-Tech (60% allocation), a more expansive toolset. The Touch intervention contrasted two training approaches—Low-Touch, a self-guided approach where patients could view built-in tutorials, and High-Touch (initially 50% allocation), where patients receive in-person guided training with the technology. The realized allocation ratios are presented in Table 2.

Table 2. Realized allocation ratio.

Tech Allocation	Touch Allocation		Total
	High	Low	
Full			
Frequency	624	1,523	2,147
Row %	29.1%	70.9%	100.0%
Column %	69.3%	76.5%	74.2%
Overall %	21.6%	52.7%	74.2%
Lite			
Frequency	277	468	745
Row %	37.2%	62.8%	100.0%
Column %	30.7%	23.5%	25.8%
Overall %	9.6%	16.2%	25.8%
Total			
Frequency	901	1,991	2,892
Row %	31.2%	68.8%	100.0%
Column %	100.0%	100.0%	100.0%
Overall %	31.1%	68.8%	100.0%

The assignment protocol used three phases where the Touch allocation ratio was changed by the research team.

1. In Phase 1, patients received the High-Touch intervention only after consenting to the study and submitting their Admission survey (see Section 3.8.2). Low-Touch patients could view the tutorial at any point and were not required to complete the Admission survey. Phase 1 assigned patients to High/Low-Touch in a 1:1 ratio.
2. In Phase 2, beginning in February 2018, the study shifted to a 3:1 ratio of High/Low-Touch. This change was done to ensure that sufficient individuals were assigned to the High-Touch intervention due to under-enrollment. Quality monitoring of the study found a number of exogenous factors that were impacting the High-Touch intervention, including, but not limited to: patient discharges; patient moved to other rooms; patient not present during TN rounding; patient was engaged with the care team and unable to work with the TN; and tablet returned prior to receiving an intervention. This change in the ratio was intended to increase the number of patients who would be eligible to receive a High-Touch intervention while maintaining the *per protocol* approach in that these exceptions were considered a component of the Protocol.

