3. Phase 3 began in March 2018 and lasted through the end of the study in September, 2018. This phase maintained the 3:1 split, but removed the requirement that patients complete the Admission survey prior to receiving the High-Touch intervention. Completion of the survey was found to limit the number of patients in the High-Touch study arm. This change represented a deviation

from the original protocol which had required that the Admission survey be completed prior to intervention delivery (see Section 4.2.1).

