3.8.2 Satisfaction and self-efficacy

Data on satisfaction and self-efficacy were collected via survey at enrollment (referred to as the Admission survey), between 10 and 21 days post-discharge (referred to as the 15-day Post-discharge survey) and, finally, at six months post-discharge (referred to as the 6-month Post-discharge survey). The three surveys each gathered data on the outcomes to allow for comparisons at different time points.

The Admission survey included questions related to self-efficacy, hospital satisfaction, and patient experience. The Admission survey was administered in two modes: a paper form and electronically. The electronic survey was created and collected using Qualtrics online survey software. Patients accessed the survey via the MyChart Bedside portal. The default administration mode was electronic; paper forms were only given if the patient requested it or encountered a technical issue with the hospital-issued tablet that affected their ability to complete the survey electronically.

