### 1.6.1 Outcome 1 – Patient satisfaction was dependent on treatment

*Outcome specification:* Variations of this outcome were available in each survey. The following 5-point Likert scale survey items were explored as individual items dichotomized to one “most positive” response versus all other responses:

- **15-day Post-discharge survey:** In your most recent hospital experience, how satisfied were you with the interactions you had with your healthcare professionals?
- **15-day Post-discharge survey:** In your most recent hospital experience, how satisfied were you with how well your healthcare professionals responded to your concerns?
- **6-month Post-discharge survey:** In the past six months, how satisfied were you with the interactions you had with your healthcare professionals?
- **6-month Post-discharge survey:** In the past six months, how satisfied were you with how well your healthcare professionals responded to your concerns?

*Statistical Model:* Logistic regression models with and without an interaction of Tech and Touch were reported.

*Covariates:* The corresponding survey item from the Admission Survey was used as a covariate for the items listed above. The two relevant survey items were:

- **Admission survey:** In the past 12 months, how satisfied were you with the interactions you had with your healthcare professional?
- **Admission survey:** In the past 12 months, how satisfied were you with how well your healthcare professionals responded to your concerns?

*Sub-sample analysis:* No sub-sample analyses were considered for this outcome.

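### Self-efficacy (H4) is analysed without the Admission score that was already collected, which gives up some precision but does not bias the result

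*SAP*

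**What the plan says.** SAP 1.8.1 scores self-efficacy as the mean of six five-point items and says the scale "was promulgated in each of the surveys (i.e. Admission, 15-day Post-discharge, 6-month Post-discharge"). Its model entry reads "OLS regression model with and without an interaction of Tech and Touch were reported", and its covariate entry reads "No covariates were added to this analysis". The section does not say which survey supplies the outcome, or whether the Admission score is a baseline.

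Elsewhere the SAP does adjust for baseline. For H2a satisfaction (SAP 1.6.1): "The corresponding survey item from the Admission Survey was used as a covariate for the items listed above". For H3b (SAP 1.7.5), the count of sessions before enrolment is a covariate. The two H2b involvement outcomes (SAP 1.6.2a and 1.6.2b) have no covariates. The offset that SAP 1.4.2 puts in all models is days of tablet provisioning, which does not adjust for baseline self-efficacy.

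Protocol 3.1.3 describes when the Admission survey was taken relative to training. At the start, "In Phase 1, patients received the High-Touch intervention only after consenting to the study and submitting their Admission survey". Phase 3, from March 2018, "removed the requirement that patients complete the Admission survey prior to receiving the High-Touch intervention". Protocol Table 1 also records an intermediate step on 22 February 2018, when Technology Navigators could mark a survey as complete so that training could go ahead.

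**The concern.** A baseline value of the same scale is usually the strongest single predictor of a follow-up score. The trial paid for it and then left it out of H4 with no reason given, while using the matching kind of covariate for H2a and H3b. The price is a wider confidence interval than necessary on a secondary hypothesis. The silence on which survey is the outcome adds a second gap: as written, the Admission score could be read as an outcome or as a baseline.

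**Working it through.** **The plan's own figure.** There is none for H4: no SD, effect size, power or sample size. Protocol 3.4 plans 3,872 patients for changes of 2.2% to 3.8% on HCAHPS satisfaction scores. That range cannot be reproduced, because baseline rates and power are not given. At 1:1 allocation, two-sided 0.05 and 80% power (all assumed), it corresponds to baseline rates near 92.5% and 75%. It does not bear on H4.

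**Inputs.** r, the correlation of Admission with follow-up score, and p, the share of analysed patients with a usable pre-training score, are not in the documents. Assumed: r = 0.4 to 0.6 and p = 0.5 to 0.75. Touch counts of 901 and 1,991 come from Protocol Table 2 and are illustrative.

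**Step 1: complete baselines.** Adjustment multiplies the variance by 1 − r². At r = 0.5 this is 0.75. Simulation with 901 v 1,991 patients gave standard errors of 0.034 adjusted and 0.040 unadjusted, with no bias.

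**Step 2: only a share p usable, the rest set to a constant.** Residual variance is p(1 − r²) + (1 − p) = 1 − p·r². Reduction in variance:

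| | r = 0.4 | r = 0.5 | r = 0.6 |
|---|---|---|---|
| p = 0.5 | 8% | 12.5% | 18% |
| p = 0.75 | 12% | 19% | 27% |

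Check by simulation at r = 0.5 with 30% missing (p = 0.7), all patients kept with a missing-score indicator: standard errors of 0.0367 and 0.0403, so the variance ratio is (0.0367/0.0403)² = 0.83. The formula gives 1 − 0.7 × 0.25 = 0.825.

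In interval width, √0.92 = 0.96 and √0.73 = 0.85, so intervals are about 4% to 15% narrower. For Touch, with everyone responding, patients independent and 80% power, the detectable difference is 2.80 × √(1/901 + 1/1,991) = 0.113 SD unadjusted. It becomes about 0.108 to 0.096 SD.

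**Step 3: why missing scores must not drop patients.** SAP 1.2 assumes data missing completely at random and does no imputation, so a regression on the score would use complete cases. Its variance relative to the unadjusted model is (1 − r²)/(1 − m), with m the missing share. This exceeds 1 once m > r²: 16%, 25% or 36% for r = 0.4, 0.5 or 0.6. At r = 0.5 and m = 30%, the simulated standard error was 0.041, against 0.040 unadjusted.

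**Step 4: why late scores must not be used.** If a share f of High-Touch Admission scores already carries the full training effect, adjustment shrinks the Touch estimate by about r × f. At r = 0.5 and f = 0.5 that is 25%. Simulation gave 0.090 against a true 0.12.

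**Step 5: the phase indicator.** The figures in step 2 are the contribution of the score, compared with the same model without it. Touch allocation moved from 1:1 to 3:1 in February 2018, so a phase term has its own cost for Touch. If half the patients enrolled at each ratio (assumed), the variance of the Touch indicator is 0.625 × 0.375 = 0.234 overall. Within phase it averages 0.5 × 0.25 + 0.5 × 0.1875 = 0.219. The ratio is 1.07; with three quarters enrolled before the change it is 1.05. The documents report no change in the Tech ratio by phase, so no such cost is expected there.

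**The case against.** The strongest case against is that the Admission score is not a clean baseline.

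- From February 2018 it could be completed during training (Protocol 4.2.1, amendment 3).
- Patients without a survey could be visited on a later admission to complete it (amendment 1), and the rules in Protocol Table 3 sometimes keep a later-admission survey. Those rules dropped few surveys (11 and 4).
- In Phase 1, Low-Touch patients did not have to complete the survey, so missing scores may differ by arm.
- Electronic surveys were reached through MyChart Bedside (Protocol 3.8.2), so some Tech exposure may come first.
- The H2a Admission items ask about the past 12 months, whereas the self-efficacy items ask about present confidence, which exposure could shift more easily. The SAP does not give this as its reason.

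All of this stands, and it decides which scores may be used. It does not justify discarding every score: the first two problems can be excluded by date, the third can be reported, and the fourth equally affects the H2a covariate that the SAP already uses. If missing scores depend both on arm and on self-efficacy, adjustment could bring in a bias that the unadjusted model lacks. That is why the unadjusted model must be kept.

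A reader might infer more than the documents support:

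- That the full r² (16% to 36% for the assumed r) is recoverable at no cost. It is not, because late scores cannot be used.
- That H4 is the only outcome left unadjusted. H2b is unadjusted too.
- That the trial fell short of its planned enrolment. The 2,892 in Protocol Table 2 is the total of the realised allocation; the text does not say whether it precedes the exclusions in Protocol 6.3.8, and the 3,872 was planned on satisfaction scores.

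**Conclusion.** The point holds as one of efficiency. A reader might infer that the unadjusted H4 estimate is biased; the omission does not make it so, and its confidence interval already reflects chance imbalance at baseline. What is lost is about p × r² of the variance. That is roughly 8% to 27% for p = 0.5 to 0.75 and r = 0.4 to 0.6, all assumed. The range is approximate because standard errors are clustered by hospital (SAP 1.4.2). For Touch, the net gain over a model with no phase term is smaller: at the low end the phase term would use up most of it (0.92 × 1.07 = 0.98). The phase term is justified by the change in allocation, not by precision. H4 is a secondary hypothesis, so this is a worthwhile, inexpensive improvement and no threat to the trial's conclusions.

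**What to change.** In SAP 1.8.1:

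1. Name the 15-day and 6-month scores as the outcomes, and add the Admission score as a covariate.
2. Use the score only for patients enrolled before the February 2018 change whose survey was completed during the enrolment admission. Protocol 6.3.3 already matches surveys to encounters by date.
3. For everyone else, including patients with no Admission score, set the covariate to the overall mean regardless of arm, so that no one is dropped.
4. Add an enrolment-phase indicator, which also reflects the move from 1:1 to 3:1 in Touch allocation.
5. Report missing Admission scores by arm, and keep the unadjusted model as a sensitivity analysis.
6. State that electronic Admission surveys were reached through MyChart Bedside and so may follow brief Tech exposure. If results are already known, label the adjusted analysis post hoc.

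The cost is a little more analysis work on data already in hand. The downsides are a modest gain of unknown size and a baseline that is not strictly pre-exposure for Tech.

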**Section 2: Changes to the Statistical Analysis Plan**

The original statistical analysis plan was specified based on assumptions about the data collection and distributions of the data, and was designed to be exploratory and flexible to account for violation of modeling assumptions. The final statistical analysis plan reflects a more detailed description of how the analyses were performed.

